### Document History

Version	Date	Change(s)	Author
0.1	04 Jun 2020	Initial Draft	[REDACTED]
0.2	15 Jun 2020	Updated per core team comments	[REDACTED]
0.3	19 Jun 2020	Updated per SMT comments	[REDACTED]
1.0	17 Jul 2020	Updated per last chance review comments	[REDACTED]

## LIST OF ABBREVIATIONS

ALT	Alanine aminotransferase
BDR	Biomarker and Discovery Research
BiG	Bioinformatics Groups
CTCAE	Common Toxicity Criteria for Adverse Events
DSMB	Data and Safety Monitoring Board
eCRF	Electronic Case Report Form
eGFR	Estimated glomerular filtration rate
GGT	Gamma-glutamyl transferase
ITN	Immune Tolerance Network
KM	Kaplan Meier
MedDRA	Medical Dictionary for Regulatory Activities
NKF	National Kidney Foundation
SAE	Serious Adverse Event
SAP	Statistical Analysis Plan
SD	Standard Deviation

## 1. PROTOCOL SYNOPSIS

Title	ALLTOL: A Prospective Cohort Study of Operationally Tolerant Allograft Recipients
IND Sponsor	NIAID
Conducted by	Immune Tolerance Network
Protocol Chair(s)	[REDACTED]
Accrual Objective	
There is no upper limit on the number of study participants, but we estimate that approximately 70 participants may be enrolled from former ITN studies and from de novo referrals.

Study Treatment	N/A
Study Design	
This trial is a multi-center, prospective, observational study in which operationally tolerant recipients of liver or kidney allografts will be followed longitudinally with annual collections of clinical data and biological samples. All participants will be followed for the duration of the trial regardless of changes in their tolerance status.
 
Participants will be recruited along three main pathways:
 

1. Tolerant participants from current and past ITN trials; including those who have already completed trial participation and those who are anticipated to complete trial participation;

2. Tolerant participants referred by ITN affiliated investigators, academic and community transplant physicians and directly through outreach to transplant affinity groups such as the National Kidney Foundation (NKF);

3. Tolerant participants from the general transplant community who are reachable through general media channels such as clinicaltrials.gov, the ITN website, word-of-mouth referrals from existing participants and social media.

 
Participants will be encouraged to complete their study visits on site. However, participants who are unable or unwilling to travel to a study site will have the option of completing their study visits remotely (Figure 1).

Study Duration	
The trial will continue through January 31, 2021.
 
On March 24, 2020 the study ended early due to the potential risk of the research participants and personnel as a result of the COVID-19 pandemic.

Primary Objective	
The primary objective of this study is to identify and longitudinally follow individuals who have received a kidney or liver transplant and who have achieved a state of operational tolerance to their allograft.
 
Operational tolerance is defined as meeting all of the criteria listed below:
 

1. Absence of biopsy-proven or clinical rejection, as determined by medical history

2. Maintenance off immunosuppressive medication, with the exception of short courses of steroids for non-allograft related conditions; e.g., asthma

3. Normal and stable allograft function (see Study Definitions). Allograft function tests used in primary endpoint calculations must be obtained in the absence of confounding factors. A Primary Endpoint Adjudication Committee (see Study Definitions) will review cases where confounding factors are suspected of having impact on the participant's test results and make recommendations toward resolution of the participant's status.

Primary Endpoint	The primary endpoint of this study is the time to loss of operational tolerance.
Secondary Endpoints	
Safety
 
The following endpoints will be assessed for all participants:
 
 
1. Time to development of de novo anti-HLA antibody or DSA
 
2. Time to the first episode of biopsy-proven or clinical acute rejection, steroid resistant rejection and chronic rejection
 
3. Time to graft loss, not including death with functioning graft
 
 
Mechanistic
 
Mechanistic endpoints will longitudinally examine the following parameters with regard to operational tolerance:
 
 
4. Time course of changes in previously identified tolerance signatures in individual participants.
 
5. Expression levels for a wide variety of genes measured by large-scale microarray or by PCR assessments.
 
6. Flow-cytometric measurements of cell populations distinguished by cell-surface phenotype.
 
7. miRNA levels in peripheral blood
 
8. Gut microbiome profile
 

Inclusion Criteria	
Participants must meet all of the following criteria to be eligible for this study:
 
 
1. Recipient of single organ liver or kidney allograft from a living or deceased donor.
 
2. At screening, operationally tolerant defined as meeting both of the following criteria: 
 
a. Absence of any immunosuppressive therapy for <math>\geq</math> 52 weeks prior to the screening visit.
 
b. No evidence of allograft rejection in the 52 weeks prior to the screening visit, based on the medical history.
 
 
 
3. Normal allograft function (see Study Definitions) If the site investigator judges that a participant exhibits stable allograft function despite values outside these criteria, then the participant is eligible if the ITN clinical trial physician/protocol chair, NIAID medical monitor and a subject matter expert concur.
 
4. Receiving regular follow up for a kidney or liver transplant by a local physician. Participants must be willing to allow the study team to contact and share medical information with this local physician.
 
5. Ability to sign informed consent.
 

Exclusion Criteria	
Participants who meet any of the following criteria will not be eligible for this study:
 
 
1. Current malignancy requiring recent surgery, ongoing chemotherapy, or radiation.
 
2. Transplant of another organ.
 
3. Current drug or alcohol dependency.
 
4. Any medical condition that in the opinion of the principal investigator would interfere with safe completion of the trial.
 
5. Inability to comply with the study visit schedule and required assessments.
 

Stopping Rules	N/A

## 2. INTRODUCTION

This statistical analysis plan (SAP) only includes analyses related to the primary and secondary clinical endpoints outlined in the protocol. Mechanistic analyses will be performed at the Immune Tolerance Network (ITN), and a separate analysis plan will be created to detail the planned analyses. Relevant clinical data from the study will be submitted to the ITN Biomarker and Discovery Research (BDR) and ITN Bioinformatics Groups (BiG) to augment the mechanistic analyses.

## 3. GENERAL ANALYSIS AND REPORTING CONVENTIONS

The following analyses and reporting conventions will be used:

- Categorical variables will be summarized using counts (n) and percentages (%) and will be presented in the form “n (%).” Percentages will be rounded to one decimal place.
- Numeric variables will be summarized using n, mean, standard deviation (SD), median, minimum (min), maximum (max). The min/max will be reported at the same level of significance as original data. The mean and median will be reported at one more significant digit than the precision of the data, and SD will be reported at two more significant digits than the precision of the data.
- The median will be reported as the average of the two middle numbers if the dataset contains an even number of observations.
- Test statistics including  $t$  and  $z$  test statistics will be reported to two decimal places.
- $P$ -values will be reported to three decimal places if greater than or equal to 0.001. If less than 0.001, the value will be reported as “<0.001.” A  $p$ -value can be reported as “1.000” only if it is exactly 1.000 without rounding. A  $p$ -value can be reported as “0.000” only if it is exactly 0.000 without rounding.
- Proportions will be expressed as percentages.
- Missing values will not be imputed unless explicitly stated.

If departures from these general conventions are present in the specific evaluations section of this SAP, then those conventions will take precedence over these general conventions.

## 4. ANALYSIS SAMPLES

The analysis sample will be comprised of all enrolled subjects that fulfill eligibility criteria and complete at least one mechanistic sample collection.

## 5. STUDY SUBJECTS

### 5.1. Disposition of Subjects

The disposition of all enrolled subjects will be summarized in tables and listed.

The numbers and percentages of subjects enrolled, screen failed, and accrued will be presented. The number and percent completing each yearly study visit as well as reasons for

early termination from the study will be presented. The breakdown of allograft type (liver vs. kidney) and previous ITN study participation vs. non-ITN study participation will also be shown.

## **5.2. Demographic and Other Baseline Characteristics**

Summary descriptive statistics for baseline and demographic characteristics will be reported for the analysis sample defined in Section 4. Characteristics to be summarized include age (at study entry and time of transplant), race, ethnicity, sex, organ type, transplant indication, time from transplant, donor type, previous ITN study participation, date of operational tolerance and time off immunosuppression.

# **6. STUDY OPERATIONS**

## **6.1. Protocol Deviations**

Major protocol deviations (site-level and subject-specific) will be listed by site and by participant with information such as type of deviation, deviation sub-type, date of occurrence, details of the deviation, and the steps taken to address the deviation.

# **7. ENDPOINT EVALUATION**

## **7.1. Overview of Efficacy Analysis Methods**

### **7.1.1. Multicenter Studies**

Study subjects will be recruited from 5 study sites. Due to the small number of subjects in the study, study data will be analyzed as a whole, and no formal accommodation for site-to-site variation will be made.

### **7.1.2. Assessment Time Windows**

Visit 0 must occur within 60 days of enrollment. Each subsequent visit must occur yearly with a +/- 60-day window.

All data will be included in analyses, regardless of time of assessment.

Furthermore, clinical data and mechanistic specimens that have already been collected from enrolled subjects from previous ITN study participation may be used to supplement the ALLTOL specimens and data, as needed.

## **7.2. Primary Endpoint**

The primary endpoint of this study is the time to loss of operational tolerance.

Operational tolerance is defined as meeting all of the following criteria:

1. Absence of rejection (biopsy-proven or clinical rejection), as determined by medical history
2. Maintenance off immunosuppressive medication, with the exception of short courses of steroids for non-allograft related conditions; e.g. asthma

3. Normal and stable allograft function. Allograft function tests used in primary endpoint calculations must be obtained in the absence of confounding factors.

### **7.2.1. Computation of the Primary Endpoint**

Normal and stable allograft function is defined as liver function tests (ALT, GGT) that have not increased more than 50% above the participant's baseline values for liver transplant recipients OR serum creatinine that has not increased more than 25% above the participant's baseline value for kidney transplant recipients.

For participants with study data that suggests the loss of operational tolerance according to the criteria in Section 7.2, the Primary Endpoint Adjudication Committee will review each case to determine if there were any potential confounding factors that may have impacted the participant's results. This committee will be comprised of the Study Protocol Chair, NIH Medical Monitor, a subject matter expert, and statistician. The following information will be presented to the committee in a blinded fashion (void of all ID and site information):

- a. Demographic and baseline characteristics (age at study entry, race, sex, ethnicity, organ type, transplant indication, age at transplant, transplant date, time from transplant, donor type, previous ITN study (Y/N), date off IS, time off IS).
- b. ALT and GGT lab values presented over time graphically for liver recipients OR creatinine values presented over time graphically for kidney recipients. A listing of each relevant lab value will also be included.
- c. All IS medication usage
- d. Any rejection event information
- e. Biliary complications or new diabetes diagnosis.

Additional information can be requested by the committee.

The committee will make a determination of each participant's tolerance status for participants with study data that suggests the loss of operational tolerance according to the criteria defined in section 7.2. The determination of the cases reviewed above will be recorded and signed off by the protocol chair and medical monitor.

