## Study Definitions Page

Adverse Event	Any untoward or unfavorable medical occurrence associated with the subject's participation in the research, whether or not considered related to the subject's participation in the research (Section 8.2.1).
Biliary Complications	Incidence of biliary complications including any of the following: 
 
• Biliary stricture requiring stenting
 
• Other evidence of biliary obstruction
 
• Cholangitis
 

Enrollment	The signing of informed consent (Section 3.1.1).
Liver Graft Loss	The incidence of any of the following: 
 
• Re-transplantation
 
• Re-listing for transplantation
 
• Participant death with a non-functioning graft
 

Normal and stable graft function	
Baseline (Values collected at screening):
 
Liver transplant recipients: Liver function tests (ALT, GGT) both less than or equal to the upper limit of normal (ULN).
 
Kidney transplant recipients: Serum creatinine value correspond to an estimated GFR > 45 ml/min/1.73 m^2.
 
Post-Baseline
 
Liver function tests (ALT, GGT) (for liver transplant recipients) that have not increased more than 50% above the participant's baseline values or serum creatinine (for kidney transplant recipients) that have not increased more than 25% above the participant's baseline values, and these tests were collected in the absence of confounding factors.

Operational Tolerance	Participants must meet all of these criteria for at least 52 weeks after the last documented dose of immunosuppressive medication: 
 
1. Absence of rejection (biopsy-proven or clinical rejection)
 
2. Maintenance off immunosuppressive medication
 
3. Normal and/or stable allograft function
 

Primary Endpoint Adjudication Committee	The Primary Endpoint Adjudication Committee is comprised of the Study Protocol Chair/ITN Clinical Trial Physician, NIH Medical Monitor, a subject matter expert, and Statistician. The Committee will review the participant's clinical history to determine whether the participant is operationally tolerant.
Renal Function	Estimated GFR calculated for adults by CKD-EPI and for pediatric participants (<18 years) by both CKD-EPI and modified Schwartz formulae  .

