### **3.1.2 Enrollment and Accrual**

Enrollment will occur on an ongoing basis through November 1, 2020. There is no upper limit on the number of study participants, but we estimate that approximately 70 participants may be enrolled from former ITN studies and from de novo referrals. Enrollment is defined as the signing of informed consent and will be obtained prior to the initiation of any screening or study mandated procedures. Enrolled participants who do not fulfill eligibility criteria or who do not complete any mechanistic sample collection for any reason will be considered screen failures. Screening values will be considered the participant’s baseline for those who meet all eligibility criteria. If a repeat assessment is needed to confirm eligibility, the repeat value will be considered the participant’s baseline value. There is no upper limit on screen failures.

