### **7.2.2. Primary Analysis of the Primary Endpoint**

The primary endpoint will be analyzed using Kaplan-Meier survival estimates and associated two-sided 95% confidence interval, using a delayed-entry model controlling for left-truncation of survival times through adjusting for the time from achieving operational tolerance to the time of study enrollment.

A participant will be considered to have lost operational tolerance if they experience rejection, have loss of stable allograft function (in the absence of confounding factors), or restart immunosuppression. The date of loss of operational tolerance (end date of operational tolerance) will be the first date on which the subject meets any of the criteria for loss of operational tolerance. Specifically,

- If tolerance is lost due to rejection, the date will equal the date of the biopsy.
- If tolerance is lost due to restarting immunosuppression, the date will equal the date of the first immunosuppression medication dosage.
- If tolerance is lost due to abnormal allograft function, the date will equal the first recorded abnormal lab date.

The time to loss of operational tolerance for all participants will be evaluated relative to time zero. Time zero will be considered 52 weeks from the participant's last documented dose of immunosuppression and in the absence of rejection or evidence for loss of normal and stable graft function since that last dose. If the exact date of the last dose is not known, the date will be imputed to the 15th of the month when the day is missing, and July 1st when both day and month are missing. The year must be known.

$$\begin{aligned} & \text{time to loss of operational tolerance} \\ & \quad = \text{end date of operational tolerance} - \text{start date of operational tolerance} \end{aligned}$$

Subjects lost to death, voluntary withdrawal or lost to follow-up will be censored at the time of occurrence of these events. Subjects who were followed until study closure (24MAR2020) without losing tolerance will be censored at the time of their most recent data point.

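### Functional loss is measured from the screening value while tolerance time runs from Time Zero, so decline before screening that stays within the entry limits is not counted and the pooled curve mixes different functional events

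*SAP*

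**What the plan says.** **The functional criterion.** SAP 7.2.1 defines normal and stable function as "liver function tests (ALT, GGT) that have not increased more than 50% above the participant's baseline values" in liver recipients, or "serum creatinine that has not increased more than 25% above" baseline in kidney recipients.

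**The reference.** The Protocol's Study Definitions label it "Baseline (Values collected at screening". Protocol 3.1.2 likewise makes screening values the "baseline for those who meet all eligibility criteria"; a repeat value replaces them if one was needed to confirm eligibility.

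**The clock.** SAP 7.2.2: "The time to loss of operational tolerance for all participants will be evaluated relative to time zero". Time Zero falls 52 weeks after the last recorded immunosuppressive dose, provided there has been no rejection and no evidence of functional loss since. Protocol 4.1 requires at least 52 weeks off immunosuppression before screening and sets no maximum.

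**Limits at entry.** Kidney: eGFR above 45. Liver: ALT and GGT no higher than the ULN. Protocol 4.1 lets a participant outside these limits enter if function is judged stable and the named parties agree.

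**Earlier data.** SAP 7.1.2 says that "clinical data and mechanistic specimens that have already been collected from enrolled subjects from previous ITN study participation may be used" to supplement ALLTOL data, but does not connect them to the baseline or the primary endpoint. SAP 7.2.3, on sensitivity analyses of the primary endpoint, is a heading with no text.

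**The concern.** The curve is meant to show how long tolerance lasts after it is reached; durability over time is secondary objective 3. Rejection and restart of immunosuppression mean the same thing whenever a person enters. The functional component does not, because its threshold is set by the value found at screening. Someone screened eight years after Time Zero is tested against the year-8 value, and someone screened near Time Zero against a value close to year 0. Both contribute to the same curve.

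The delayed-entry estimator corrects for who is under observation at each time since Time Zero. It assumes that the event is the same for everyone in the risk set, and it cannot restore that when the event definition moves with the entry date.

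Gradual functional decline is a course that long follow-up of these recipients should be able to show. If part of it falls before the reference value, and the rest has only a few years in which to reach the threshold, a reader could take the curve as evidence of functional stability since Time Zero that was never measured.

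**Working it through.** The documents give no event rate, power or drift figure, so there is no stated number to reproduce.

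**1. Same course, different event.** Assume creatinine rises 3% a year from Time Zero. Time to a 25% rise is ln 1.25 / ln 1.03 = 7.5 years from whichever reference is used.

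| Screened at year | Creatinine at screening ÷ Time Zero value | Plan's limit ÷ Time Zero value | Year the plan's limit is crossed |
|---|---|---|---|
| 0 | 1.00 | 1.25 | 7.5 |
| 4 | 1.03^4 = 1.126 | 1.407 | 11.5 |
| 8 | 1.03^8 = 1.267 | 1.583 | 15.5 |

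None of the three has an event within the five scheduled years (1.03^5 = 1.159). Against a Time Zero reference, the second would have an event at the year-8 visit (1.267) and the third would already be past 25% at screening.

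**2. Decline that fits inside the kidney entry limit.** With creatinine above κ, the CKD-EPI formula in SAP 7.5 makes eGFR proportional to creatinine^(−1.209). With age held fixed, the creatinine ratio is (eGFR at Time Zero ÷ eGFR at screening)^(1/1.209).

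- 80 to 50: 1.6^(1/1.209) = 1.475, a 48% rise.
- 90 to just above 45: 2^(1/1.209) = 1.774, a 77% rise.
- 75 to just above 45: 1.526, a 53% rise.
- 60 to just above 45: 1.269, a 27% rise.

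The formula also has an age factor of 0.993 per year. If eight years pass, 80 to 50 becomes (1.6 × 0.993^8)^(1/1.209) = 1.408, a 41% rise, and 60 to 45 becomes 1.211, which is below 25%. The larger falls exceed the limit either way; the smallest does so only over a short gap.

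From eGFR 45, a further 25% rise multiplies eGFR by 1.25^(−1.209) = 0.764, giving about 34, before the plan records functional loss.

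**3. Drift needed after screening.**

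- Creatinine, 25%: 1.25^(1/5) − 1 = 4.6% a year over five years; 1.25^(1/3) − 1 = 7.7% over three.
- ALT or GGT, 50%: 1.5^(1/5) − 1 = 8.4% a year over five years; 1.5^(1/3) − 1 = 14.5% over three.

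The reference is fixed at screening, so faster drift does accumulate to an event: 5% a year reaches 25% at 4.6 years and 10% a year at 2.3 years.

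**4. Illustrative simulation, creatinine criterion only.** All inputs are assumed: 20,000 participants; annual visits for five years; eGFR 55 to 100 at Time Zero and above 45 at entry; entry uniform over 0–10 years; no laboratory noise. Drift is on the log scale per year. The true value is the share of the population whose creatinine has not passed 1.25 times its Time Zero value.

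| Mean drift (SD) | Already past 25% at entry | 5-year: true / screening ref. / Time Zero ref. | 10-year: true / screening ref. / Time Zero ref. |
|---|---|---|---|
| 0.01 (0.02) | 6% | 0.957 / 0.997 / 0.977 | 0.728 / 0.957 / 0.756 |
| 0.03 (0.03) | 20% | 0.681 / 0.934 / 0.772 | 0.396 / 0.681 / 0.431 |
| 0.05 (0.03) | 31% | 0.434 / 0.838 / 0.550 | 0.180 / 0.442 / 0.210 |

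With entry over 0–3 years, 0% to 3% were already past 25%, and the noise-free 5-year estimates (screening / Time Zero reference) were 0.996 / 0.976, 0.908 / 0.750 and 0.783 / 0.517. The 5-year ordering was the same in every run, with or without noise. It should not be read into the far tail: with entry over 0–3 years nobody is observed after year 8 (3 + 5), and carrying the curve to year 10 gave 0.145 against 0.244 at drift 0.03 without noise, with a true value of 0.402.

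Adding within-person log SD 0.08 (entry 0–10 years), the 5-year screening-reference estimate against the true value was 0.881 v 0.957, 0.774 v 0.686 and 0.668 v 0.430: too low at the smallest drift, too high at the other two.

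**The case against.** **The plan has safeguards.** The Time Zero definition excludes evidence of functional loss, Protocol 9.2.4 collects past episodes of allograft dysfunction, and the entry limits remove some decliners. A reader might infer that all decline before enrollment is erased; the documents do not support that. What escapes is relative decline that stays within the limits. The plan's only percentage rule for stability refers to the screening value, scheduled laboratory tests begin at screening, and a history of episodes need not reveal gradual drift. For liver, the ULN requirement narrows the gap considerably, apart from the exception route.

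**Slow decline can still be an event.** A reader might infer that it never can. That is wrong, because the reference does not move after screening and increments add up. Functional loss is delayed, and missed only when follow-up ends before the total reaches 25% or 50%.

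**The direction of bias is not fixed.** SAP 7.2.2 dates functional loss at the first abnormal laboratory value, so noise can create events. A liver recipient with low-normal ALT or GGT can exceed 50% while still within normal. Committee review addresses confounding factors, not noise as such. This objection stands against any flat statement that durability is overstated.

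**The study is observational, with no hypothesis test.** True, and it limits the severity. It does not settle what the durability curve may be said to show.

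**Conclusion.** The mismatch between reference and clock is in the documents, and delayed entry does not remove it. A kidney recipient whose creatinine rose by 41% to 48% between Time Zero and screening (eGFR 80 to 50, with or without eight years of ageing) can enter event-free under a 25% rule, unless the history happens to show the loss. After entry, steady creatinine drift below about 4.6% a year stays uncounted over five years.

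Under assumed upward drift, the screening reference gave higher 5-year retention than a Time Zero reference in every run. That is a comparison between two definitions. Whether the plan's curve lies above true durability depends on drift, laboratory noise and entry times, none of which the documents give. The simulated figures show the mechanism and should not be quoted as the size of bias in this cohort. They cover creatinine only and leave out rejection and restart of immunosuppression, which do not depend on the baseline value.

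The SAP should be changed: the remedy is inexpensive and determines what the primary curve can support.

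**What to change.** Keep the composite primary endpoint on the Time Zero clock; putting its components on different clocks would leave no single time-to-first-event curve.

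1. **SAP 7.2.2.** State that the functional criterion is re-baselined at enrollment, and that the curve estimates freedom from rejection, from restart of immunosuppression and from functional change since screening. Limit the durability conclusion to that. State which reference value and laboratory source, if any, support the Time Zero condition on function.
2. **SAP 7.2.3, sensitivity analysis.** For participants with earlier ITN laboratory values, repeat the primary analysis using the value nearest Time Zero as reference. Report how many have such a value, how far from Time Zero it was taken, and how many were already beyond 25% or 50% at screening.
3. **SAP 7.2.3, supplementary description.** Report the functional component alone, timed from the screening baseline.

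**Cost.** SAP text, one sensitivity analysis and one descriptive analysis, with no new visits. The limitation is coverage: item 2 reaches only participants with values near Time Zero. The documents permit use of earlier ITN data but do not confirm that such values exist, and they name no laboratory source near Time Zero for non-ITN referrals.

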## 9. STATISTICAL CONSIDERATIONS AND ANALYTICAL PLAN

### 9.1 ANALYSIS SAMPLE

The analysis sample will be comprised of all enrolled subjects that fulfill eligibility criteria and complete at least one mechanistic sample collection. Furthermore, clinical data and mechanistic specimens that have already been collected from enrolled subjects from previous ITN study participation may be used to supplement the ALLTOL specimens and data, as needed.

In addition, the following subset analyses will be performed on all study endpoints:

- a. allograft type (liver vs kidney)
- b. previous ITN study participation vs non-ITN study-referral

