## 7.4. Examination of Subgroups

In addition, the following subset analyses will be performed on all study endpoints where the data permits:

- a. Allograft type (liver vs. kidney)
- b. Previous ITN study participation vs. non-ITN study referral

All subgroup analyses will be descriptive in nature.

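### The adjudication packet shows previous ITN participation, a planned subset variable, although the plan gives that flag no role in judging confounding

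*SAP*

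**What the plan says.** SAP 7.2.1 sends every participant whose data suggest a loss of operational tolerance to the Primary Endpoint Adjudication Committee. The case information "will be presented to the committee in a blinded fashion (void of all ID and site information". That parenthesis is the only definition of blinding given. Item (a) of the packet, the demographic and baseline block, includes "previous ITN study (Y/N), date off IS, time off IS" as well as the transplant date and the time from transplant.

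The committee's task is "to determine if there were any potential confounding factors that may have impacted the participant's results". Its ruling settles the endpoint: "The committee will make a determination of each participant's tolerance status for participants with study data that suggests the loss of operational tolerance".

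SAP 7.4 plans subset analyses of all study endpoints, where the data allow, by allograft type and by "Previous ITN study participation vs. non-ITN study referral". Protocol 9.1 plans the same split, "previous ITN study participation vs non-ITN study-referral", and protocol 3.3.1 repeats it. SAP 7.4 adds: "All subgroup analyses will be descriptive in nature".

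**The concern.** The committee sees the variable that defines a planned subset analysis of the outcome it decides. Only participants with an apparent loss are reviewed, so a ruling either confirms an event or removes one. If knowledge of previous ITN participation made members more or less ready to accept a confounding explanation, the event count would shift in one subset and not in the other. Part of any ITN versus non-ITN difference in time to loss of tolerance would then come from the endpoint process rather than from the participants.

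What is at stake is the reading of one of two planned subset analyses of the primary endpoint. No hypothesis test and no decision rule depends on it.

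**Working it through.** The plan gives no figure to reproduce on this point, so the check is mainly a comparison of sections.

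1. **What is withheld.** Participant ID and site (SAP 7.2.1). Nothing else.
2. **What is shown.** Previous ITN participation as yes/no, organ type, transplant date, date off immunosuppression and the matching intervals. The packet also holds laboratory values over time, all immunosuppressive use, rejection information, and biliary or new diabetes events (SAP 7.2.1, items a to e).
3. **Where the flag is used in analysis.** It defines the second subset split in SAP 7.4, protocol 3.3.1 and protocol 9.1. The split applies to all endpoints, so it includes the adjudicated primary endpoint.
4. **Whether judgement enters.** Restarting immunosuppression and biopsy-proven rejection leave little room for it. The laboratory thresholds are numeric: more than 50% above baseline for ALT or GGT, and more than 25% for creatinine. Whether a rise was confounded is a judgement, because the SAP gives no rule for what counts as a confounder. Protocol 6.3 names dehydration and infection, but only as examples and only for screening tests.
5. **Whether the flag is needed.** Organ type, the other subset variable, has to be visible because the tests and thresholds differ by organ. Neither document gives previous ITN participation any part in judging confounding.
6. **Whether a safeguard is stated.** None was found. The SAP heading for sensitivity analyses of the primary endpoint (7.2.3) has no text under it, and no analysis of unadjudicated events is planned elsewhere.

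**Scale of one ruling (illustration).** Inputs: N of about 70 (protocol 9.3). The documents do not give the split by ITN status, so an ITN share of 30% to 70% is assumed.

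- Subset sizes: 0.30 × 70 = 21 and 0.70 × 70 = 49. An even split gives 35 and 35.
- Change in a subset's crude loss proportion when one case is ruled the other way: 1/n.
- 1/49 = 2.0 points; 1/35 = 2.9 points; 1/21 = 4.8 points.

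These are crude proportions. The planned estimate is a delayed-entry Kaplan-Meier curve, where the effect of one event depends on the number at risk at that time. The figures show how much one ruling weighs. They are not an estimate of bias.

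**The case against.** The strongest reply is that the plan does what it says. A reader might infer that calling the review blinded while showing the ITN flag is a contradiction. It is not: the SAP defines blinding in the same sentence as the removal of ID and site, and the listed fields contain neither. There are no treatment arms, so there is no allocation to conceal. This stands, and the point is only that the blinding is narrower than it could be.

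A reader might also infer a bias of known direction and size. Suppose 10 apparent losses in each subset of 35, with 50% excused in one and 30% in the other. That gives 5/35 = 14.3% against 7/35 = 20.0%, a gap of 5.7 points with no true difference. Every input is assumed, so the gap only restates the assumption. Nothing in the documents suggests that members would favour either group.

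A third tempting reading is that members could identify individuals from the transplant date and other fields in a cohort of about 70. This is possible, but the documents do not show it.

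The flag may also have a use. SAP 7.1.2 and protocol 9.1 allow earlier ITN data to supplement the study data, so the field could tell members where a participant's history came from. Neither document says so. If that is the purpose, it should be stated.

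Finally, deleting one field would not fully mask ITN status. Medication history may reveal it, and the committee may request more information. The protocol chair/ITN clinical trial physician, the medical monitor and a subject matter expert also rule on eligibility exceptions (protocol 4.1), so some cases may already be known to people in those roles. This stands as a limit on the benefit. It is not a reason to show the field.

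**Conclusion.** The point holds as a minor, inexpensive improvement. The packet shows a subset variable to the people who judge the endpoint, the plan gives no reason for showing it, and no safeguard is stated. That leaves an avoidable route to differential adjudication between the ITN and non-ITN subsets.

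Its reach is limited. It concerns a descriptive subset analysis, done where the data permit, and mainly the cases flagged on laboratory values. The whole-cohort primary estimate involves no ITN comparison, and no type I error or formal inference is affected. The documents show no evidence of bias, no direction and no size. The range of 2.0 to 4.8 points per ruling rests on N of about 70 and an assumed ITN share of 30% to 70%.

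**What to change.** Delete the previous-ITN-study field from item (a) of the packet in SAP 7.2.1. If it serves a purpose in judging confounding, state that purpose instead. The cost is one field in a report, and the committee can still ask for more information.

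Optionally, replace calendar dates with days from time zero throughout the packet. Removing dates outright would make it harder to line up laboratory values with immunosuppression, rejection and biliary events; relative days keep that alignment. The cost is a small amount of programming.

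The SAP is dated July 2020, after the study closed on 24 March 2020, and the documents do not say whether adjudication had been done. If cases have already been reviewed with the flag visible, say so in the report. Then repeat the ITN subset analysis on unadjudicated criteria as a sensitivity check under SAP 7.2.3: recorded rejection, restarted immunosuppression, or a laboratory value over the stated threshold, with no committee exclusions. That version will count confounded rises as losses, so its use is to show whether the ITN versus non-ITN picture changes, not to replace the adjudicated result. It needs one extra run on data already collected.
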